2 STUDY OBJECTIVES

2.1 Primary Objective(s)

The primary objective of the study is to assess the sensitivity and specificity of rhPSMA-7.3 (¹⁸F) positron emission tomography (PET) in detecting N1 disease (as determined by the central BIE) on a patient level compared to the histopathology of pelvic lymphatic tissue removed during RP and PLND. At least one positive pelvic LN on PET (N1) and one positive LN as determined by histopathology (pN1) on the same side of the pelvis (left or right) will be deemed a True Positive (TP) at the patient level. In patients who have no TP regions (left or right), the translation of varying combinations of False Positive (FP), True Negative (TN) and False Negative (FN) regions to patient level categorizations is described in detail in Section 4.13.

2.2 Secondary Objective(s)

The secondary objectives of the study are:

1. To assess the Verified Detection Rate (VDR) for M1 disease of rhPSMA-7.3 (¹⁸F) PET findings (as determined by central BIE) on a patient level in patients with newly diagnosed unfavorable intermediate-, high-, or very high-risk PCa using histopathology or confirmatory imaging.
2. To assess the VDR for M1 disease of rhPSMA-7.3 (¹⁸F) PET findings (as determined by central BIE) on a patient level in patients with negative conventional imaging.
3. To assess the positive predictive value (PPV) of rhPSMA-7.3 (¹⁸F) PET for N1 and M1 lesions (as determined by central BIE) compared to histopathology or confirmatory imaging (M1 lesions only).
4. To assess the PPV of rhPSMA-7.3 (¹⁸F) PET for detecting pelvic LN metastases compared to surgical pathology on a patient level in which a FP patient is defined as having at least one FP region (right or left pelvis), regardless of any coexisting TP findings.
5. To assess the negative predictive value (NPV) of rhPSMA-7.3 (¹⁸F) PET for detecting pelvic LN metastases compared to surgical pathology on a patient level in which a FN patient is defined as having at least one FN region (right or left pelvis), regardless of any coexisting TN findings.
6. To assess the impact of rhPSMA-7.3 (¹⁸F) PET BIE on a) upstaging patients planned for RP or b) converting planned RP to external beam radiation therapy (EBRT).

PAREXEL International

Blue Earth Diagnostics
BED-PSMA-301

Statistical Analysis Plan

7. To determine the inter- and intra-reader agreement of rhPSMA-7.3 (¹⁸F) scan interpretation by blinded independent readers.

8. To assess the safety of rhPSMA-7.3 (¹⁸F) injection in patients.

2.3 Exploratory Objective(s)

The exploratory objectives of the study are:

1. To assess the sensitivity and specificity of rhPSMA-7.3 (¹⁸F) PET in detecting nodal metastases (as determined by central BIE) on a regional level compared to the histopathology of pelvic lymphatic tissue removed during RP and PLND.

3 INVESTIGATIONAL PLAN

3.1 Overall Study Design and Plan

This is a prospective, Phase 3, multi-center, single-arm, diagnostic imaging study designed to evaluate the safety and diagnostic performance of rhPSMA-7.3 (¹⁸F) PET ligand for the detection of N1 and M1 metastases in men with newly diagnosed unfavorable intermediate-, high- or very high-risk PCa (per NCCN Guidelines Version 1.2020; PROS-2).

Up to approximately 375 patients will be enrolled into the study to ensure inclusion of at least 300 evaluable patients undergoing RP and PLND. Consented patients will be screened at Visit 1 to determine eligibility for the study up to 28 days (up to 45 days due to the Coronavirus Disease-2019 [COVID-19] pandemic) before Investigational product (IP) administration at Visit 2. Due to the COVID-19 pandemic, Visit 1 and Visit 2 may be combined. Patients who meet all of the inclusion criteria and none of the exclusion criteria will be assigned a patient identifier (ID) and entered into the study at screening. In addition to their routine clinical work-up, which may include ^{99m}technetium-biphosphonate and abdominal/pelvic computed tomography (CT) or magnetic resonance imaging (MRI) and chest CT per local practice, and before the scheduled RP, patients will be administered a dose of rhPSMA-7.3 (¹⁸F), an administered activity of 8 mCi (296 MBq) \pm 20% delivered as an intravenous (IV) bolus injection with a 10 mL fast 0.9% sodium chloride flush, followed by PET imaging.

Note: The screening/eligibility evaluation may take place on the day of rhPSMA-7.3 (¹⁸F) administration (with pre-screening via telephone), if necessary, to ensure the safety of enrolled patients (see Visit 1 and 2 combined; CSP Section 10.3). Alternatively, the time from Visit 1 (initial screening) to Visit 2 (rhPSMA-7.3 (¹⁸F) PET scan) may be extended to 45 days due to the COVID-19 pandemic.

The PET imaging results for each patient will be reported to the responsible physician prior to the planned RP. If safe and feasible, within 1 to 3 days post-IP administration, the patient must return to the clinic for safety follow-up including an electrocardiogram (ECG), blood safety laboratory tests and a focused physical examination. Clinical review of the imaging results and discussion of further procedures/treatments with the patient should also take place at this visit if the results are available. In cases where the rhPSMA-7.3 (¹⁸F) PET imaging results are not available at the safety

PAREXEL International

Blue Earth Diagnostics
BED-PSMA-301

Statistical Analysis Plan

follow-up visit, imaging results and further procedures/treatment plan should be discussed with the patient within 7 days after rhPSMA-7.3 (¹⁸F) imaging (this review may be conducted by telephone at the clinician's discretion). Note: due to the COVID-19 pandemic, the post-IP safety follow-up (laboratory and ECG assessments and focused physical examination) may be conducted within 1 to 5 days post-IP administration to ensure the safety of enrolled patients.

Within 45 days post-IP administration (may be extended to 60 days due to the COVID-19 pandemic), the patient will receive treatment as follows, with further detail provided in CSP Section 9.1.6.

- Standard of care surgical treatment of PCa, including a PLND; or
- If the rhPSMA-7.3 (¹⁸F) PET scan detects M1 lesion(s):
 - A biopsy/surgery and/or additional imaging to confirm M1 lesion(s) will be required prior to initiation of treatment.

Safety will include adverse events (AEs) and vital signs monitoring, clinical laboratory evaluations, 12-lead ECG and focused physical examinations performed in all patients.

3.2 Endpoints

3.2.1 Primary Efficacy Endpoint

The co-primary endpoints for this study will be the:

- Sensitivity of rhPSMA-7.3 (¹⁸F) PET (as determined by central BIE) for detecting pelvic LN metastases compared to surgical pathology on a patient level.
- Specificity of rhPSMA-7.3 (¹⁸F) PET (as determined by central BIE) for detecting pelvic LN metastases compared to surgical pathology on a patient level

3.2.2 Secondary Efficacy Endpoints

The secondary endpoints for this study will be:

1. Percentage of patients in whom rhPSMA-7.3 (¹⁸F) imaging detects at least one verified M1 metastasis, as determined by central BIE.
2. Percentage of patients with negative conventional imaging for M1 disease in whom rhPSMA-7.3 (¹⁸F) PET detects at least one verified M1 metastasis, as determined by central BIE.
3. Patient level PPV of rhPSMA-7.3 (¹⁸F) PET BIE for N1 and M1 lesions compared to histopathology or confirmatory imaging (M1 lesions only).
4. PPV of rhPSMA-7.3 (¹⁸F) PET for detecting pelvic LN metastases compared to surgical pathology on a patient level in which a FP patient is defined as having at least one FP region (right or left pelvis), regardless of any coexisting TP findings.
5. NPV of rhPSMA-7.3 (¹⁸F) PET for detecting pelvic LN metastases compared to surgical pathology on a patient level in which a FN patient is defined as having at least one FN region (right or left pelvis), regardless of any coexisting TN findings.
- 6.

PAREXEL International

Blue Earth Diagnostics
BED-PSMA-301

Statistical Analysis Plan

- a. The percentage of patients being upstaged to N1 or M1 disease;
- b. The percentage of patients in whom planned RP is converted to EBRT.

7. Kappa statistic for the agreement between and within blinded independent readers on the interpretation of rhPSMA-7.3 (¹⁸F) scans.

8. Safety (AEs, vital signs clinical laboratory evaluations, 12-lead ECG and focused physical examinations) of rhPSMA-7.3 (¹⁸F) injection in patients

3.2.3 Exploratory Efficacy Endpoints

1. Diagnostic performance (sensitivity and specificity) of rhPSMA-7.3 (¹⁸F) PET for detecting pelvic LN metastases compared to surgical pathology on a regional level.

3.2.4 Safety Variables

In all patients, safety evaluations will include AE monitoring and reporting from the time of informed consent throughout the study.

Vital sign assessments will also be conducted at screening and pre- and post-IP administration on the day of rhPSMA-7.3 (¹⁸F) injection.

In addition, a focused physical examination will be performed at screening and at the safety follow-up visit within 1 to 3 days post-IP administration (may occur within 1 to 5 days post-IP administration due to the COVID-19 pandemic), and a 12-lead ECG will be performed pre-IP administration on the day of rhPSMA-7.3 (¹⁸F) injection and at the safety follow-up visit within 1 to 3 days post-IP administration (may occur within 1 to 5 days post-IP administration due to the COVID-19 pandemic). Baseline blood safety laboratory tests, including hematology (full blood count), biochemistry (urea and electrolytes, liver function tests) and coagulation will be performed pre-IP administration on the day of rhPSMA-7.3 (¹⁸F) injection and repeated at the safety follow-up visit within 1 to 3 days post-IP administration (may occur within 1 to 5 days post-IP administration due to the COVID-19 pandemic).

4 STATISTICAL METHODS**4.1 Data Quality Assurance**

All tables, figures and data listings to be included in the report will be independently checked for consistency, integrity and in accordance with standard Parexel procedures.

4.2 General Presentation Considerations

‘Baseline’ is defined as the last available pre-IP administration assessment.

‘End of Study’ is defined as the last available post-IP administration assessment.

PAREXEL International

Blue Earth Diagnostics
BED-PSMA-301

Statistical Analysis Plan

'Study Day' will be calculated relative to the date of rhPSMA-7.3 (¹⁸F) injection day, and is equal to:

- Assessment Date – IP Administration Date + 1 if the assessment date is on or after IP administration date.
- Assessment Date – IP Administration Date, if the assessment date is before IP administration date.

Continuous data will be summarized in terms of the mean, standard deviation (SD), median, minimum, maximum and number of observations, unless otherwise stated. Continuous data (e.g. counts) that are expected to be skewed will be presented in terms of the maximum, upper quartile, median, lower quartile, minimum and number of observations. The minimum and maximum will be reported to the same number of decimal places as the raw data recorded in the database. The mean, median, lower quartile and upper quartile will be reported to one more decimal place than the raw data recorded in the database. The SD will be reported to two more decimal places than the raw data recorded in the database. In case the rules result in more than four decimal places, the number of decimal places reported shall be four for any summary statistic, irrespective of the previous rules.

Categorical data will be summarized in terms of the number of patients providing data at the relevant time point (n), frequency counts and percentages. Any planned collapsing of categories will be detailed in the SAP text and the data displays.

Percentages will be presented to one decimal place. Percentages will not be presented for zero counts. Percentages will be calculated using n as the denominator. If sample sizes are small, the data displays will show the percentages, but any textual report will describe frequencies only.

Changes from baseline in categorical data will be summarized using shift tables where appropriate.

P-values greater than or equal to 0.001, in general, will be presented to three decimal places. P-values less than 0.001 will be presented as “<0.001”.

Confidence intervals (CIs) of continuous variables will be presented to one more decimal place than the raw data. CIs of proportions will be presented to three decimal places (e.g. 1/3 will be a proportion of 0.333) and exact intervals (Clopper-Pearson) will be employed unless specified otherwise. CI for percentages will be to one decimal place.

4.3 Software

All report outputs will be produced using SAS® version 9.3 or a later version in a secure and validated environment.

4.4 Study Patients

4.4.1 Disposition of Patients

A clear accounting of the disposition of all patients who enter the study will be provided, from screening to study completion as per CONSORT guidance.

The following summaries will be provided:

- A summary of the number of patients screened for entry into the study and the number and percentage of patients excluded prior to IP administration by major reason and overall (Analysis set: All enrolled Patients)
- A summary of the number of patients enrolled (See section 4.5) per center, and per country (Analysis set: Full Analysis Set [FAS]).
- A summary of the number of patients who received IP, number of patients who had an evaluable PET scan following IP administration, and the number and percentage of patients withdrawing from the study and completing each phase. (Analysis set: FAS).
- A summary of withdrawals from the study and from IP administration by major reason (Analysis set: FAS).

By-patient listings of eligibility details, enrollment details, visit dates (including impact of COVID-19 on visits), withdrawal/study completion details (including reason for discontinuation and time since IP administration prior to discontinuation) will be provided.

4.4.2 Protocol Deviations

Protocol deviations will be handled in accordance with Parexel Standard Operating Procedures (SOPs).

Protocol deviations occur when the patient, investigator, or Sponsor fails to adhere to protocol requirements or where there is a significant non-compliance to ICH-GCP, affecting patient safety or the scientific value of the trial.

Major protocol deviations are defined as those deviations from the protocol likely to have an impact on the perceived efficacy and/or safety of study treatments. The impact of major protocol deviations on the efficacy and/or safety results will be investigated by assessing the robustness of the study results and conclusions to the choice of analysis set, both including and excluding data potentially affected by major protocol deviations at a Data Review Meeting (DRM) shortly before database lock. Results and population assignments will be summarized in a DRM report which will be signed off by all relevant scientific experts.

Major protocol deviations and any action to be taken regarding the exclusion of patients or affected data from specific analyses are defined in the project-specific Protocol Deviation Specification which is agreed and signed off before analysis.

Major protocol deviations which lead to withdrawal and replacement of the patient include, but not limited to:

PAREXEL International

Blue Earth Diagnostics
BED-PSMA-301

Statistical Analysis Plan

- Failure to meet inclusion/exclusion criteria (see CSP Sections 6.2 and 6.3).
- Use of a prohibited concomitant medication (see CSP Section 7.1).
- IP administration but no subsequent PET scan.
- Significant non-compliance with IP administration.

Patients will be withdrawn from the study and be included in the All Enrolled Patients and Full Safety Population as applicable.

Deviations due to COVID-19 will be listed separately.

A by-patient listing of major protocol deviations will be provided.

A summary of the number and percentage of patients with a major protocol deviation by type of deviation (Analysis set: FAS) will be provided.

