4.5 Analysis Sets

All enrolled patients: all patients who signed the informed consent form.

Full Analysis Set (FAS): all patients who were scheduled to receive the rhPSMA-7.3 (¹⁸F) injection having met the inclusion/exclusion criteria.

Full Safety Population (FSP): all patients who received the rhPSMA-7.3 (¹⁸F) injection.

Efficacy Analysis Population (EAP): all patients who received rhPSMA-7.3 (¹⁸F) injection followed by a PET/CT scan and who underwent RP and PLND.

Extended Efficacy Population (EEP): all patients who received rhPSMA-7.3 (¹⁸F) injection followed by a PET/CT scan. This population includes M0 and M1 patients independent of performance of RP and PLND and will be used for M1 related efficacy and Kappa statistics.

Per Protocol Population (PP): All patients in the EAP population who have histology available from surgery that allows SoT determination, and without any major protocol deviations that will affect the evaluations of the PET scan or histology.

The primary analysis will be based on the EAP. The FSP will be used for all safety summaries.

Upon database release, protocol deviation and analysis set outputs will be produced and will be to BED for review. An analysis set classification meeting will be arranged to discuss the outputs and to decide which patients and/or patient data will be excluded from certain analyses. Decisions made regarding the exclusion of patients and/or patient data from the analyses, and the agreement of population inclusion for each patient, will be made prior to database lock and will be documented and approved by the Sponsor.

A by-patient listing of analysis set details will be provided. This listing will include: center, country, patient identifier, and inclusion/exclusion flag for each set and reason for exclusion from

PAREXEL International

Blue Earth Diagnostics
BED-PSMA-301

Statistical Analysis Plan

each set. All enrolled patients will appear on this listing. If patient data have been partially excluded, visit will also appear on this listing.

The number and percentage of patients in each population will be provided using all enrolled patients.

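### The SAP places the with/without-deviation comparison of results before database lock, while exclusions are still being decided, and does not withhold the central reads or their match with histology from those deciding

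*SAP*

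**What the plan says.** SAP 4.4.2 defines major deviations as those likely to affect the perceived efficacy or safety of the study treatment. Their impact is to be examined by "assessing the robustness of the study results and conclusions to the choice of analysis set, both including and excluding data potentially affected". The SAP sets the time for this work: it is to happen "at a Data Review Meeting (DRM) shortly before database lock". What the meeting produces is then described: "Results and population assignments will be summarized in a DRM report which will be signed off by all relevant scientific experts".

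The same section says that major deviations, and the resulting exclusions, are defined in a project-specific Protocol Deviation Specification signed off before analysis. It also lists deviations that lead to withdrawal and replacement. The list is expressly not exhaustive, and patients withdrawn under it are assigned only to All Enrolled Patients and the Full Safety Population.

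SAP 4.5 names the EAP as the primary set. It is defined by injection, PET/CT scan, RP and PLND, with no deviation criterion. The PP set further requires usable histology and no major deviation affecting evaluation of the scan or the histology. On process, 4.5 says: "Upon database release, protocol deviation and analysis set outputs will be produced". A classification meeting then discusses these outputs "to decide which patients and/or patient data will be excluded from certain analyses". Those decisions "will be made prior to database lock and will be documented and approved by the Sponsor".

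The study is open-label (protocol 8.2). The masking described applies to the image readers (protocol 9.1.6 and 9.1.8).

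**The concern.** In a single-arm study judged against fixed performance goals, the result is credible only if the patients counted are settled without knowing how each choice moves the result. Read literally, 4.4.2 puts results with and without the affected data in front of a meeting held before lock, and reports them alongside the population assignments. Section 4.5 keeps exclusions open until lock. Neither section says that those who decide lack access to the central reads, the histology or their cross-classification.

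At stake are membership of the PP set, on which the primary analysis is repeated (SAP 4.14.2), and any removal from the EAP through the open-ended withdrawal list in 4.4.2 or the exclusions allowed in 4.5. This question of order is separate from the question of which set a deviating patient belongs to. Settling the second would still leave results on the table before lock.

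**Working it through.** **Inputs.** From SAP 4.14.2: one-sided 0.025 exact binomial tests, goals of 22.5% (sensitivity) and 82.5% (specificity), and success only if both goals are met by the same two of three readers. From SAP 4.16: 75 positive and 225 negative cases, assumed true values of 40% and 90%, and 90% power for each. The documents give no expected number of deviating patients, so every flagged count below is an assumption.

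**1. The plan's own figures.** The pass mark r is the smallest count with P(X ≥ r | n, p0) ≤ 0.025.
- Sensitivity, n = 75: r = 25, actual alpha 0.0207, power at 40% = 0.904.
- Specificity, n = 225: r = 197, actual alpha 0.0246, power at 90% = 0.906.

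Both reproduce the stated 90%.

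**2. How few exclusions matter (one reader).** Take a miss by one case.
- Sensitivity: 24/75 gives p = 0.037. Removing three false negatives gives 24/72, p = 0.023.
- Specificity: 196/225 gives p = 0.038. Removing two false positives gives 196/223, p = 0.018.

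**3. Type I error, one reader, sensitivity, true value 22.5%.** Let m of the 75 positives be flagged, independently of the read. A ~ Bin(75 − m, 0.225) counts detections among unflagged patients, and B ~ Bin(m, 0.225) counts them among flagged patients.

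(a) Better of including or excluding all flagged patients: P(A + B ≥ r(75) or A ≥ r(75 − m)).

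(b) Dropping only the flagged false negatives, of which there are m − B: P(A + B ≥ r(75 − (m − B))).

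| Flagged m of 75 | (a) better of two | (b) flagged FN dropped |
|---|---|---|
| 0 | 2.1% | 2.1% |
| 4 (5%) | 2.4% | 3.1% |
| 8 (11%) | 2.5% | 4.3% |
| 15 (20%) | 2.8% | see step 4 |

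The analogue of (a) for specificity, with 5–15% excluded at random, gives 2.8–2.9% against 2.5%.

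**4. Under the study's success rule.** This was simulated at sensitivity 22.5% and n = 75, with correlated readers (latent-normal model), agreement assumed and specificity taken as always met. In (b), the patients dropped are flagged patients whom the majority of readers missed.

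| Assumed kappa | No choice | (a) 4–15 flagged | (b) 4 flagged | (b) 8 flagged |
|---|---|---|---|---|
| about 0.46 | 0.8% | 1.0–1.2% | 1.2% | 1.6% |
| about 0.69 | 1.3% | 1.6–1.8% | 1.9% | 2.6% |

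A repeat simulation of (a) gave about 0.8–1.6%. With 15 flagged, (b) gives 3.7–5.9% across the two agreement levels. If readers agreed perfectly, two of three would reduce to one reader, and the step 3 figures would apply.

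**The case against.** The strongest reply is that the plan already contains most of the control.

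- **The primary set is fixed.** The EAP is pre-named and defined by events, and success is not declared on the PP set. A reader might infer that the primary population can be chosen freely once results are known. The documents do not support that.
- **Exclusions are meant to follow rules.** They are to be defined in a Protocol Deviation Specification signed before analysis. That specification, the SOPs and the Independent Review Charter are not among the documents reviewed and may contain masking. The withdrawal grounds actually listed (eligibility, prohibited medication, no scan, non-compliance with administration) do not depend on reads or histology.
- **The 4.5 meeting has named inputs.** They are deviation and analysis-set outputs, not efficacy results. A reader might also take the DRM and the classification meeting to be one event. The SAP does not say so.
- **The 4.4.2 sentence may be loose drafting.** It may merge the post-lock PP repeat with a routine deviation review.

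Much of this stands, and it narrows the exposure. It does not remove it. Sign-off before analysis is not stated to precede the DRM, and the DRM itself, as written, looks at results. The withdrawal list is open-ended, and 4.5 does not exempt the primary analysis from its exclusions. Decisions are due before lock, but the outputs that feed them appear on an undefined database release. The SAP also states in its Introduction that it supersedes the protocol where they differ, so its literal wording governs.

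**Conclusion.** The point holds in limited form. As written, results with and without deviating data are assessed before lock, while exclusions are still open and with no stated masking. The exposure covers PP membership and removal from the EAP by withdrawal or exclusion, not a free choice of primary set.

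A reader might infer that the 0.025 level is broken. That is not shown for the include/exclude choice. It reaches 2.4–2.8% for one reader and sensitivity alone, but about 0.8–1.8% under the two-of-three rule at the agreement levels tried. Selective removal of false negatives exceeds 2.5% for one reader (3.1–4.3% with 4–8 flagged). Under the two-of-three rule it does so only with more flagged patients or higher agreement, for example 2.6% with 8 flagged at kappa about 0.69. That scenario also means removing only failures, which a signed rule-based specification should prevent.

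All these figures rest on assumed flagged counts, flagging unrelated to the read, and assumed reader agreement. The two-of-three figures also take specificity as met, which overstates the chance of overall false success. The main cost is therefore to the credibility of the pre-specified sets. Nothing here suggests that anyone intends to select on results.

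**What to change.** Amend SAP 4.4.2 and 4.5 to state that:

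1. the Protocol Deviation Specification, including its exclusion rules, is signed before the DRM;
2. the DRM and the classification meeting work only from deviation and analysis-set listings, with central reads and reads-versus-SoT classifications withheld;
3. set membership is signed and the database locked before any result is computed with and without the affected data;
4. that comparison is then run as a post-lock robustness analysis.

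In the same edit, say whether the two meetings are one, and reconcile database release with database lock. Protocol section 14 says that major deviations will be defined in the SAP, so the SAP should either contain those definitions or explain why a separate document holds them.

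The cost is SAP wording and the order of existing steps. Sample size, alpha, power, endpoints and patient procedures do not change.

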16.1 Data Sets Analyzed

All enrolled patients: all patients who signed the informed consent form.

Full Analysis Set (FAS): all patients who were scheduled to receive the rhPSMA-7.3 (¹⁸F) injection by meeting the inclusion/exclusion criteria.

Full Safety Population (FSP): all patients who received the rhPSMA-7.3 (¹⁸F) injection.

Efficacy Analysis Population (EAP): all patients who received rhPSMA-7.3 (¹⁸F) injection with a PET scan and who got through RP and PLND.

Per Protocol Population (PP): All evaluable patients in the EAP population.

The primary analysis will be based on the EAP. The FSP will be used for all safety summaries.

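### Read literally, the major-deviation table cannot show an eligibility violation, because it runs on a set limited to men who met the criteria; the FAS dosing and withdrawal counts have the same gap

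*SAP*

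**What the plan says.** Three parts of the plan meet here.

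- **Deviations (SAP 4.4.2).** Four types of major deviation are listed as leading to withdrawal and replacement. The first is "Failure to meet inclusion/exclusion criteria (see CSP Sections 6.2 and 6.3"). The others are prohibited medication, no PET scan after the investigational product (IP), and significant non-compliance with IP administration. A routing sentence follows: "Patients will be withdrawn from the study and be included in the All Enrolled Patients and Full Safety Population as applicable". It does not mention the FAS. The only deviation summary is then set on the FAS: "A summary of the number and percentage of patients with a major protocol deviation by type of deviation (Analysis set: FAS) will be provided".
- **Set definitions (SAP 4.5, protocol 16.1).** The FAS holds men scheduled for the "injection having met the inclusion/exclusion criteria". The protocol has the same condition: "injection by meeting the inclusion/exclusion criteria". The FSP is everyone injected, with no eligibility condition. All Enrolled is everyone who signed consent.
- **Disposition (SAP 4.4.1).** One summary opens "A summary of the number of patients who received IP, number of patients who had an evaluable PET scan following IP administration" and ends by covering "patients withdrawing from the study and completing each phase. (Analysis set: FAS"). Another is "A summary of withdrawals from the study and from IP administration by major reason (Analysis set: FAS"). The only disposition summary on All Enrolled covers men screened and men excluded before dosing.

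**The concern.** A deviation table should show, among other things, how many men were let in who should not have been. Here the set chosen for the table is defined by the absence of that deviation. A reader who sees a zero in the eligibility row would take it as a finding, when on the literal wording it is a consequence of the definition.

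The disposition tables share the problem. SAP 4.4.1 sets out to account for every patient from screening to completion. Yet a man who is injected and then found ineligible is not counted as dosed or withdrawn in the FAS summaries, and the All Enrolled summary counts only exclusions before dosing. The number shown as having received IP can therefore be smaller than the denominator of the safety tables, with no summary row that explains the difference.

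Such cases are foreseeable. Protocol 13.2 provides for withdrawing men in whom an exclusion criterion arises or comes to light after entry, and protocol 10.3 allows screening and injection on the same day.

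**Working it through.** The plan gives no figure for this point, so there is nothing to reproduce. The check is set logic, followed by a count with an assumed input.

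**Set logic, literal reading**

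1. Let V be the men who failed an eligibility criterion. By SAP 4.5, membership of the FAS requires having met the criteria, so V and the FAS have no member in common.
2. The SAP 4.4.2 table counts deviations within the FAS. Eligibility row = number in both V and FAS = 0, for any size of V.
3. The FSP has no eligibility condition. If k members of V were injected, then received IP on the FAS = FSP − k.
4. The SAP 4.4.1 withdrawal summaries also omit these k men, although SAP 4.4.2 says that they are to be withdrawn.

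**Count**

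Inputs: about 375 men planned (SAP 4.16). I take all 375 as dosed, for illustration. The documents do not give k, so the values below are assumptions and not estimates.

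| k (assumed) | Eligibility row on FAS: 0/(375 − k) | Same row on FSP: k/375 | Received IP on FAS | FSP |
|---|---|---|---|---|
| 0 | 0/375 | 0/375 (0.0%) | 375 | 375 |
| 4 | 0/371 | 4/375 (1.1%) | 371 | 375 |
| 8 | 0/367 | 8/375 (2.1%) | 367 | 375 |
| 19 | 0/356 | 19/375 (5.1%) | 356 | 375 |

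The FAS column cannot tell these four situations apart by its numerator.

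**The other three rows**

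The FAS definition says nothing about prohibited medication, a missing PET scan or IP non-compliance, so by definition alone those men stay in the FAS and can be counted. The routing sentence in SAP 4.4.2 covers all four types, however, and names only All Enrolled and the FSP. If it is exhaustive, those three rows are emptied too. If it is not, only the eligibility row is affected. The text does not settle which.

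**Where the men can still be found**

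- SAP 4.4.1: by-patient listings of eligibility and of withdrawal or completion.
- SAP 4.4.2: a by-patient listing of major deviations, with no analysis set stated.
- SAP 4.5: a listing of all enrolled patients with a flag for each set and the reason for exclusion, and the size of each population on all enrolled.

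**The case against.** The strongest counter-argument is that the FAS condition can be read as eligibility judged at the time of scheduling. Protocol 4.1 enters men into the study at screening once they meet the criteria, and protocol 13.2 expects some problems to surface later. On that reading a man found ineligible afterwards stays in the FAS and the row is not forced to zero. The reading is possible, but the wording in SAP 4.5 is unqualified, and the routing sentence in SAP 4.4.2 points away from it. The SAP has to say which reading applies.

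A second argument is that taking the routing sentence as exhaustive would empty every named row of a table planned by type of deviation, so it was probably not meant as a rule for leaving the FAS. That is a fair reason for caution about the other three rows. It does not rescue the eligibility row, which is empty by the FAS definition alone.

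A third is that the listings and population counts already disclose these men. This stands, and it limits the point to the summary tables. It does not make a zero in a summary table correct.

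A fourth concerns the remedy. All Enrolled includes men who signed consent and were never dosed. As the sole denominator of the deviation table it would dilute every percentage with screen failures. This also stands, and it is why the FSP is the better main denominator for that table. Men excluded before dosing are already summarised by reason on All Enrolled in SAP 4.4.1.

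Finally, population assignments are to be recorded in the Data Review Meeting report, and exclusion rules in the Protocol Deviation Specification. Neither was available here. They may resolve the matter in practice, but the SAP text does not.

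**Conclusion.** The point holds as an internal contradiction with a reporting consequence. On the literal wording, the only summary of major deviations shows 0 eligibility violations for any true number, and the received-IP count in SAP 4.4.1 falls short of the FSP by the number of ineligible men dosed. The size in patients is unknown, because the documents give no rate. The conclusion rests on reading the FAS condition as finally determined eligibility.

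A reader might infer more than the documents support:

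- **That violators would be hidden from the report.** They would not. The listings and population counts keep them visible.
- **That efficacy or safety results are affected.** They are not. The primary analysis uses the Efficacy Analysis Population, the safety summaries use the FSP, and neither definition contains the FAS eligibility condition. Relabelling these tables changes no estimate, test or interval.
- **That some 8 to 19 men are at issue.** Values in that range only illustrate the arithmetic. Only dosed violators create the mismatch with the FSP.
- **That all four deviation rows are empty.** That follows only if the routing sentence is exhaustive, which the text does not state.

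This is a minor point, worth correcting because a stated rule would produce a wrong reported count and the correction is cheap.

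**What to change.** 1. In SAP 4.4.2, run the major-deviation summary on the FSP, so that dosed men are the denominator, and show an All Enrolled count beside it.
2. In SAP 4.4.1, run the received-IP, evaluable-scan, completion and withdrawal summaries on All Enrolled. Received IP then equals the FSP by definition.
3. In SAP 4.5, state whether eligibility for the FAS is as judged at scheduling or as finally determined. Word the routing sentence in SAP 4.4.2 to match, and say whether it is a complete list of the sets that keep these men.

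The cost is small edits to the SAP text and the table shells. The deviation table may look less favourable than it would under the present wording.
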